Given the rarity and novelty of CDG, the geographic spread of affected individuals, the broad clinical spectrum, the limited retrospective attempts at natural history studies (focused on one disorder or limited to one site), there is a significant **knowledge gap** regarding the progression and clinical variation in this group of disorders. Even for PMM2-CDG, preliminary data from an unpublished study emphasized that there is a need for prospective natural history studies to validate and expand on retrospective, limited results. This gap impedes the development of novel targeted therapeutics since there is no clear outcome measure for clinical trials, and it will be difficult to determine efficacy of a therapy over natural history.

Study Design and Methods

Methods:

Enrollment:

We will recruit and enroll patients with CDG in this study evaluating clinical variation and natural history when a patient is being seen as part of routine clinical care. We will invite eligible subjects to participate in the study to consent, enroll, and collect baseline data. We may also send consent forms in the mail to participants to consent or reconsent. All subjects for this study will be provided a consent form describing this study and providing sufficient information for subjects to make an informed decision about their participation in this study. This consent form will be submitted with the protocol for review and approval by the IRB for the study. The formal consent of a subject, using the IRB-approved consent form, must be obtained before that subject undergoes any study procedure. The consent form must be signed by the subject or legally acceptable surrogate, and the Investigator designated research professional obtaining the consent.

Study Activities:

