Participants will then be seen at the study sites for annual follow up visits to undergo assessments, with a variable window of 2 months. We will collect data from local providers, collect relevant medical data, and complete study forms at annual follow up visits. We will strive to minimize duplicate tests. The clinical assessment data will be obtained with each visit according to the specific CDG type and diagnosis and appropriate to standard of care. Data will be collected from the patient's medical records and through surveys for the patient and assessments given by the provider. Included in this data set is a food record recorded by the patient. This may be given by paper, or electronically (through ASA24 program). If given electronically, the patient will be sent a password via email to log into the site (this will only be sent to patients/guardians on the study who are not infants/children consuming infant/pediatric formulas and are eating normal diets). The site will ask for the patient to select which food has been consumed over a period of time and automatically calculate nutrition data that can be used for analysis. For those patients who are consuming pediatric/infant formula, we will utilize Metabolic Pro program, since formula information is not available in the ASA24 platform. Metabolic Pro will also be used for dietary calculations when food records are recorded via paper instead of electronically.

Surveys and evaluations to complete at each visit include the Nijmegen CDG rating scale (NPCRS; completed by physician through medical interview process), the PROMIS questionnaire (Patient Reported Outcomes survey, or PROs, completed by patient/family), physical examination (completed by physician), vitals (according to standard of care, completed by clinic staff), food record (completed by patient/family, on paper or electronically), and goal attainment score (three goals on a five point scale, completed by physician and family members in unison).

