A list of retrospective data to be collected from the medical record is attached to the application. Optional blood, stool, and urine samples will be collected for research at each annual visit (once per year over the course of 5 years of follow up). If a participant is unable to provide urine, stool, or blood samples due to age or other logistical difficulty, we will forego research sample collection and rely purely on clinical/research data collected over the course of the study. If any clinical residual samples (urine, blood, or stool) are available for these participants unable to provide fresh research collections, we may use these instead. These clinical residuals would come from the Biochemical Genetics Lab (BGL) at Mayo or from participating sites' laboratories, if any sample remains. Skin biopsies will be only taken for diagnostic purposes. Leftover tissue material from clinical diagnostics will be used for biomarker discovery. If a subject doesn't complete regular follow up appointments, we will reach out to them via phone or email to obtain follow up information and complete questionnaires to ensure we are able to obtain accurate follow up information. Participants will be offered up to \$700 reimbursement to cover lodging and travel expenses, per visit at all sites except for the University of Minnesota Masonic Children's Hospital. University of Minnesota will offer \$75 per visit to each participant as remuneration and will not offer travel reimbursement.

Accrual:

Our goal is to enroll 150 patients of all ages and from all CDG types over 5 years in the natural history study. At least 50 of the 150 enrolled subjects will have a diagnosis of PMM2-CDG. There will be no exclusion based on sex, ethnicity or socio-economic status. The sample size of 100 was based on a count of the number of affected individuals currently clinically followed and current patient census taken by CDG CARE in August of 2018.

Participating Sites:

We will collaborate with other sites on this study with Mayo Clinic acting as the IRB of record. The target accrual in total will remain at 150 participants. The sites below will be included in the study:

1. Children's Hospital of Pittsburgh at University of Pittsburgh Medical Center – PI is [name]
2. Seattle Children's Hospital – PI is [name]
3. Tulane University Medical School – PI is [name]
4. Baylor College of Medicine – PI is [name]
5. University of Minnesota Masonic Children's Hospital – PI is [name]

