With the data collected over time, the average trend with age will be estimated using mixed effects models to account for the correlation of repeated measures from a subject. The model will include fixed and random effects for the intercept and slope (age). Maximum likelihood estimates (MLE) will be obtained for regression coefficients for fixed effects and restricted MLE for the variance component. The association of a factor of interest with a response variable will be examined using mixed effects models to account for the subject specific change. For a time constant factor, the model will include the factor, age and an interaction term between the factor and age as fixed effects. The model will also include random effects for the intercept and slope (time). For a time varying factor, the model may include baseline value of the factor and the change at the next visit as fixed effects to estimate cross-sectional and longitudinal effects simultaneously.

We will compare results of PROs to NPCRS subdomain scores, physical exam findings, and laboratory findings that should be reflected in that tool to assess the validity of each PRO measure. Partial least squares (PLS) regression analysis will be utilized to identify patterns of association between the PROs and the clinical scores. The PLS analysis and significant weights may reveal novel composite scores for CDG patients. Changes in PRO scores over time will be tested for association with Quality of Life questions using random effects generalized linear regression models incorporating a random intercept for each participant. We will also compare subsequent scores on the PROs from the same subject to determine reliability of the PRO if there has been no significant interval change in the clinical status. Reliability will be assessed by the weighted Kappa to account for the ordinal variables.

Expected Outcomes.

References:

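### The single age slope in the trend model mixes between-patient and within-patient change; the plan should report the within-patient slope beside it

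*Combined protocol and SAP*

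**What the plan says.** All model statements are in the combined protocol and SAP, Data Analysis Plan.

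- Trend model: "the average trend with age will be estimated using mixed effects models", and then "The model will include fixed and random effects for the intercept and slope (age"). It has no term for age at enrolment or years since enrolment, and no check of linearity.
- Model for a time-constant factor: the fixed effects are the factor, age and their interaction. For the random part, "The model will also include random effects for the intercept and slope (time").
- Model for a time-varying factor: as an option, the baseline value and the later change may enter as separate terms "to estimate cross-sectional and longitudinal effects simultaneously". This is the only such split in the plan, and it is not applied to the age trend.

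The Background describes a knowledge gap "regarding the progression and clinical variation in this group of disorders" and says that, with this gap, "it will be difficult to determine efficacy of a therapy over natural history".

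The Accrual section plans 150 patients of all ages. On the schedule, Study Activities says "Participants will then be seen at the study sites for annual follow up visits". Research samples are taken "once per year over the course of 5 years of follow up", and the Biospecimens section gives up to five visits.

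**The concern.** Write a patient's age at a visit as age at enrolment plus years since enrolment. The first part differs between patients, and the second changes within a patient. A single age coefficient forces both parts to have the same slope. If the true slopes differ, the estimate is a compromise whose weights depend on the spread of entry ages, the variance components and the number of visits.

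This matters for one use of the result. A natural history that is to serve as a yardstick for a therapy needs the yearly change within a patient. The trend model does not report that change separately, so a reader cannot tell whether the pooled trend stands for it.

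Equal slopes cannot be taken for granted. Aim 1 studies case-fatality, so older entrants are survivors. The Background also says that manifestations vary across the lifespan and that sequencing has changed which disorders are identified. These features make a difference plausible but do not show one.

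**Working it through.** The plan gives no slope, variance or precision figure for this model, so there is no figure to reproduce.

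**Inputs.** From the documents: N = 150, with annual values at up to five visits. Assumed: entry ages uniform over 0 to 20 years (variance 20²/12 = 33.3), intercept SD 1, random-slope SD 0.1 per year, residual SD 0.5, complete visits, and uncorrelated random intercept and slope. Three visits stand for shorter follow-up. Slopes are in outcome units per year.

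**Target of the single slope.** If the mean is α + β_B × (entry age) + β_W × (years since entry), the generalised least squares age slope has expectation w × β_B + (1 − w) × β_W. As an estimate of β_W its bias is w × (β_B − β_W), which is zero if the slopes are equal.

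**Weight by hand, random slope on time.** w = I_B / (I_B + I_W). I_B is the entry-age variance divided by the variance of a patient's fitted baseline level given the fitted slope. I_W is 1 / (slope variance + residual variance / sum of squares of time).

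- Five visits: the sum of squares of time is 10, so I_W = 1/(0.01 + 0.25/10) = 1/0.035 = 28.6. The conditional variance is 1.15 − 0.05²/0.035 = 1.079, so I_B = 33.3/1.079 = 30.9. Then w = 30.9/59.5 = 0.52.
- Three visits: the sum of squares is 2, so I_W = 1/(0.01 + 0.25/2) = 1/0.135 = 7.4. The conditional variance is 1.208 − 0.125²/0.135 = 1.093, so I_B = 30.5. Then w = 30.5/37.9 = 0.80.

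**Standard error of the within-patient slope.** √(0.035/150) = 0.0153 at five visits and √(0.135/150) = 0.0300 at three.

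**Random slope on age.** Here the weight needs the full matrix calculation, w = slope element of (X′V⁻¹X)⁻¹X′V⁻¹a, with a the entry ages. With uncorrelated random effects it also depends on where age is zero, so uncentred age and age centred at 10 years are both shown.

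**Break-even.** The single slope has mean squared error SE_single² + w²d² for β_W, where d is the slope difference. This equals SE_within² at d = √(SE_within² − SE_single²)/w. Example, five visits, uncentred age: √(0.0153² − 0.0135²)/0.300 = 0.0072/0.300 = 0.024.

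| Visits | Random slope on | w | SE single | SE within | Break-even d | Bias if d = 0.05 (assumed) |
|---|---|---|---|---|---|---|
| 5 | uncentred age | 0.30 | 0.0135 | 0.0153 | 0.024 | 0.015 |
| 5 | centred age | 0.40 | 0.0129 | 0.0153 | 0.020 | 0.020 |
| 5 | time | 0.52 | 0.0106 | 0.0153 | 0.021 | 0.026 |
| 3 | uncentred age | 0.67 | 0.0184 | 0.0300 | 0.035 | 0.034 |
| 3 | centred age | 0.76 | 0.0163 | 0.0300 | 0.033 | 0.038 |
| 3 | time | 0.80 | 0.0133 | 0.0300 | 0.033 | 0.040 |

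**Range.** At five visits, with entry ages from 0–10 to 0–40, slope SD 0.05 to 0.2 and intercept SD 1 to 2, w runs from about 4% to 63% on uncentred age and from about 5% to 89% on time. A different set of assumptions gives 17% to 95% with a middle case of 66%. That set has entry-age SD 5 to 15 years, intraclass correlation 0.5 to 0.9, slope SD 0 to 0.10 outcome SD per year, and a random slope on centred age.

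**Power to see a difference.** The break-even value equals the standard error of the slope difference. For 80% power d must be 2.80 times that: about 0.06 to 0.07 per year at five visits and 0.09 to 0.10 at three.

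**The case against.** The strongest reply is that the plan promises an average trend with age and delivers one. Neither aim asks for a yearly within-patient rate. Progression appears in the Background as a gap in the field, and no sentence says that this slope will be the comparator for a therapy. This stands, and it limits the point to an added estimate. It does not remove it: the analysis plan itself says that the data will allow longitudinal changes to be analysed, and it already accepts the cross-sectional versus longitudinal split for other covariates.

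A second reply is that the single slope may be the better estimate even of the within-patient rate. Below the break-even differences this is true, and no document shows on which side the study lies. Hence both estimates should be reported, rather than one replacing the other.

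Third, almost every input to the size is assumed. This also stands. Dated retrospective values, if they enter the model, would reduce the mixing: ten annual values per patient (assumed) give about 6% on uncentred age and 29% on time.

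Fourth, time in the factor model may be loose wording for age. It may be, and a one-line clarification would settle it.

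A reader might infer that the planned slope is wrong, or is presented as a progression rate. The documents support neither: it is a valid description of the cohort and is called a trend with age. A reader might also infer from the five-visit rows on age that the model is mostly within-patient. That rests on unstated choices: the weight moves from 30% to 40% on centring alone, and further under other variances.

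**Conclusion.** The point holds as a low-cost improvement that should be made. The mixing follows from the stated model, and the plan neither checks nor reports whether the two slopes agree. Its size is not fixed by the documents. Under the base assumptions about a third to a half of the weight at five visits, and two thirds to four fifths at three, falls on the between-patient slope. No claim should be made about which component dominates. Whether any bias follows depends on a slope difference for which the documents give no evidence either way. If the slopes are equal there is no bias, and the pooled slope is the more precise estimate. Confidence is medium, because the mechanism is certain and the consequence is not.

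**What to change.** In the Data Analysis Plan:

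1. Keep the pooled age trend as a description of the cohort.
2. Add a model with age at enrolment and years since enrolment as separate fixed effects. Report the within-patient slope as the longitudinal estimate, the cross-sectional slope beside it, and their difference with a 95% CI. State that a non-significant difference will not be read as equality.
3. Name one time scale for the random slope in both the trend and the factor model. State its centring and use an unstructured covariance for the random intercept and slope, so that the result does not depend on where age is zero.
4. Optionally, as sensitivity analyses, add a spline for age at enrolment and an interaction of entry age with years since enrolment.

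The change needs SAP wording and no new patients, visits or data. The price is precision: under the assumed inputs the standard error of the within-patient slope is about 0.015 against 0.011 to 0.014 for the single slope at five visits, and 0.030 against 0.013 to 0.018 at three. The optional interaction costs more. With a spline, the standard error at entry age 10 is about 0.024 at five visits and 0.047 to 0.048 at three.

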Since so many biologic functions depend upon correct protein and lipid glycosylation, clinical CDG manifestations are widely variable within and among subtypes and across the lifespan. The clinical findings in affected individuals reflect glycosylation's role in the embryology and biology of many organ systems. Clinical findings may include developmental delay/intellectual disability with abnormalities in brain MRI, hypotonia, failure to thrive or growth impairment, hepatopathy, coagulopathy, immunodeficiency, protein losing enteropathy, osteopenia, skeletal dysplasias, renal abnormalities, functional and/or anatomic eye involvement, endocrinopathies, and peripheral neuropathy. Some CDG present with only tissue-specific symptoms such as SEC23B-dyserythropoietic anemia or Leukocyte Adhesion Deficiency Type II.⁶

Of the known 137 glycan-synthesis disorders we have potential therapies for only 8 disorders and not all current therapies are fully effective. Clinical trials have not validated these treatments for safety and efficacy. MPI-CDG has been treated with oral mannose.⁷ In SLC35C1-CDG, some patients respond to oral fucose supplementation. This treatment is only effective for the typical recurrent infections with hyperleukocytosis and does not correct the neurological issues of these patients.⁶ PIGM-CDG, the mutation described in the only published case so far, causes histone hypoacetylation at the PIGM promoter. Butyrate controls the seizures.⁸ PGM1, a critical enzyme for the

conversion of glucose-1-phosphate to glucose-6-phosphate, is at the crossroads of the glycogen, glucose and galactose pathway. **PGM1 deficiency is treatable with D-galactose**, alleviating the hypoglycemia, coagulopathy, and endocrinopathy seen in this disorder,^{9,10} although not the cardiomyopathy. The glycosylation defect CAD-CDG has been treated with uridine.^{11,12} Magnesium can improve MAGT1-CDG. Manganese and D-galactose have been used to treat TMEM165-CDG, whereas **SLC35A2-CDG has been treated with D-galactose**. From the group of disorders of de-glycosylation preclinical trials suggested positive effect of **GlcNAc treatment in NGLY1** deficiency.

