This protocol and any amendments will be submitted to a properly constituted independent Institutional Review Board (IRB), in agreement with local legal prescriptions, for formal approval of the study conduct. The decision of the IRB concerning the conduct of the study will be made in writing to the Investigator and a copy of this decision will be provided to the sponsor before commencement of this study. The Investigator should provide a list of IRB members and their affiliate to the sponsor upon request.

Confidentiality:

Participant confidentiality is strictly held in trust by the participating investigators, their staff, and the sponsor(s) and their agents. This confidentiality is extended to cover testing of biological samples and genetic tests in addition to the clinical information relating to participants. Therefore, the study protocol, documentation, data, and all other information generated will be held in strict confidence. No information concerning the study or the data will be released to any unauthorized third party without prior written approval of the sponsor. This study is funded by the NIH, and as such, has a Certificate of Confidentiality.

Study Monitoring:

Following written standard operating procedures, the monitors will verify that the human subject research is conducted, and data are generated, documented (recorded), and reported in compliance with the protocol, Good Clinical Practice, and the applicable regulatory requirements (e.g., Good Laboratory Practices (GLP), Good Manufacturing Practices (GMP)).

The investigational site will provide direct access to all study related sites, source data/documents, and reports for the purpose of monitoring and auditing by the NIH, and inspection by local and regulatory authorities.

Subject Information

Target accrual: 150 total: including a minimum of 50 subjects diagnosed with PMM2-CDG

Subject population (children, adults, groups): all ages

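### The average-trend and time-constant factor models assume change is linear in age across a cohort of all ages, with no nonlinear term and no check

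*Combined protocol and SAP*

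**What the plan says.** The Data Analysis Plan describes four longitudinal models. Two of them carry an age slope.

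- **Average trend.** The plan states that "the average trend with age will be estimated using mixed effects models", and then "The model will include fixed and random effects for the intercept and slope (age" in brackets. The fixed part is one intercept and one slope.
- **Time-constant factor.** "For a time constant factor, the model will include the factor, age and an interaction term between the factor and age as fixed effects". The random part is worded differently: "The model will also include random effects for the intercept and slope (time" in brackets, where the trend model has age.

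The other two state no age slope:

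- **Time-varying factor.** "For a time varying factor, the model may include baseline value of the factor and the change at the next visit as fixed effects".
- **Change in patient-reported outcomes against quality of life.** "random effects generalized linear regression models incorporating a random intercept for each participant".

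Subject Information gives "Subject population (children, adults, groups): all ages", and there are no exclusion criteria. The Background says that "clinical CDG manifestations are widely variable within and among subtypes and across the lifespan", without giving a rate or a shape. The plan contains no polynomial, spline, age band or test of linearity.

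**The concern.** A single slope says that a patient changes by the same amount per year in infancy, adolescence and adulthood. That is a strong assumption for disorders whose listed features include developmental delay and growth impairment, and the plan neither justifies nor tests it. Each patient contributes about five annual visits at most, so the curve over the lifespan is pieced together from patients of different ages. Patients are recruited as they present for routine care, and no age quotas are stated.

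Two results are at stake. The first is the natural-history slope. The Background gives the lack of natural-history data as the reason why the efficacy of a therapy is hard to judge. A slope that depends on the enrolled age mix is a poor comparator for a therapy tested in one age group. The second is the factor-by-age test. If the factor groups differ in age, each group samples a different stretch of the same curve. Two straight lines through those stretches have different slopes even when the factor does nothing.

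**Working it through.** The documents give no slope, standard deviation, significance level or age distribution for these models, so there is no planned figure to reproduce. The size was examined by simulation.

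**Inputs from the documents.** 150 patients; a factor split of 50 to 100, matching the minimum of 50 PMM2-CDG patients (Accrual); annual visits, up to 5 (Biospecimens); the fixed effects of the two models above.

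**Assumed inputs.** 2 to 5 visits per patient; right-skewed entry ages with mean about 11 years, capped at 45; between-patient SD 4; slope SD 0.3 per year; residual SD 1.5; a two-sided 5% Wald test; REML fits. The random slope was placed on time and on age in turn, because the plan names both. There were 250 trials per scenario, so the Monte Carlo standard error is √(0.05 × 0.95 / 250) = 1.4 points at 5% and √(0.5 × 0.5 / 250) = 3.2 points at 50%. The factor has no effect in any scenario.

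**Step 1: the yearly change.** For a course with pace b1 before a break and b2 after it, the fitted slope is approximately b2 + w(b1 − b2). The weight w depends on the age mix.

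- Break at age 6, true change 1.0 then 0.1 per year: the line gave 0.21–0.25, so w = (0.211 − 0.1)/0.9 = 0.12 to (0.245 − 0.1)/0.9 = 0.16. Early change is understated by about 0.75–0.79 per year, and later change is reported at 2.1–2.5 times its true value.
- Break at age 10, true change 0.8 then 0.2: the line gave 0.38–0.42, so w = (0.376 − 0.2)/0.6 = 0.29 to (0.422 − 0.2)/0.6 = 0.37.
- Smooth course 12(1 − exp(−age/8)), with local slope 1.5 exp(−age/8), which is 1.17 at age 2, 0.43 at 10 and 0.12 at 20: the line gave 0.32–0.40. It equals the local slope at age 8 ln(1.5/slope), roughly 10.5 to 12.4 years. It is too low before that and too high after.

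**Step 2: false factor-by-age findings.** Rejection rates are shown with the random slope on time / on age. The nonlinear term used here was a linear spline shared by both groups, with knots at 3, 6, 12 and 20 years.

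| True course | Group ages | Planned line | Nonlinear age term | Mean interaction per year, planned line |
|---|---|---|---|---|
| Linear, 0.4 per year | same | 5.2% / 6.4% | 5.2% / 5.6% | 0.001 |
| Linear, 0.4 per year | means about 7 and 14 | 4.8% / 4.8% | 6.0% / 7.2% | −0.003 |
| Break at 6 | same | 8.0% / 8.4% | 5.2% / 5.6% | 0.004 |
| Break at 6 | means about 7 and 14 | 47.2% / 44.8% | 6.0% / 7.2% | 0.158 |
| Break at 10 | same | 8.8% / 8.0% | 6.0% / 6.8% | 0.006 |
| Break at 10 | means about 7 and 14 | 56.4% / 52.8% | 4.8% / 6.4% | 0.184 |
| Smooth | same | 11.6% / 7.6% | 5.6% / 6.4% | 0.009 |
| Smooth | means about 7 and 14 | 76.0% / 61.2% | 5.6% / 6.8% | 0.245 |

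The planned line holds its level when the course is linear, and the nonlinear term restores it when the course is not. Functional form is therefore the cause.

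**Step 3: sensitivity to the assumptions.** A sharper course (1.5 per year to age 8, then 0; intercept SD 4, slope SD 0.5, residual SD 2; 150 replicates, REML) rejected 13% with equal ages and 77% with unequal ages. A smaller check with other assumed values (60 replicates per scenario, REML) rejected 18–22% with equal ages and 73–83% with unequal ages. With a spline its rates were 10% and 8–10%. The direction is stable; the size depends on the assumed course.

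**The case against.** The strongest defence is that this is a descriptive natural-history protocol with no stated significance level. It calls its target an average trend and leaves analysis to the data coordinating centre. On that view a single slope is a legitimate summary, and the coordinating centre can look for curvature. Part of this stands: the slope is a valid age-mix average. But the plan does not say that it is only that, and general reliance on the centre's expertise does not provide for curvature.

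A reader might infer three stronger claims that the documents do not support.

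- *That every longitudinal model is affected.* Only two of the four state an age slope.
- *That the yearly change is wrong at every age.* That is true of a course with two distinct paces. A smooth course is fitted correctly near one age.
- *That curvature will be reported as a factor-by-age association.* A large error needs both a nonlinear course and a factor related to age. Such a relation is plausible for subtype or severity, but the documents give no ages by factor. With equal age mixes the mean interaction is close to zero and the excess rejection is modest.

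Error rates are also higher if the covariance is treated as known. For the sharper course above they were 23% and 86%, against 13% and 77% with REML. The plan specifies restricted maximum likelihood for the variance components, so the REML figures are the relevant ones.

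**Conclusion.** The point holds for the average-trend model and the time-constant factor model. Both prespecify linearity in age over all ages, without a check. If the course changes pace, the reported slope depends on the age mix and misleads for most single age groups. If a factor is also related to age, a false interaction can follow: about 45–76% rejection at a nominal 5% with mean ages of about 7 and 14 years, about 8–12% with equal age mixes, and about 5–7% with a shared nonlinear age term. These sizes rest on assumed courses, ages and standard deviations. If the true course is linear, the planned models behave properly. Outcomes already scored against age norms were not examined. This should be changed before analysis, but it does not undermine the design.

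**What to change.** In both models, replace the linear fixed main effect of age with a prespecified nonlinear term, for example a restricted cubic spline with knots at fixed age quantiles. Keep the random intercept and slope, and state the same time scale for the random slope in both models or explain why they differ. Test factor-by-age with the main age effect modelled by the spline. Report a test of linearity and the average yearly change by age band, with the bands fixed in advance (for example 0–5, 6–12, 13–17 and 18 or over).

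The cost is a revision of the analysis text and a few more fixed-effect parameters (about four with four interior knots). No change to visits, sample size or data collection is needed. If the course is truly linear, age-specific slopes are less precise. In one simulation with assumed values (40 replicates), the standard errors for two age bands were 0.12 and 0.07, against 0.03 for the single slope, or about 4 and 2.3 times as large. The single slope can still be reported alongside in that case.
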